4.2 METHOD OF TREATMENT ASSIGNMENT AND BLINDING

This is an open-label (unblinded) study in which all subjects will be assigned to receive the same treatment, i.e., atezolizumab.

4.3 STUDY TREATMENT

The investigational medicinal product (IMP) for this study is atezolizumab.

4.3.1 Formulation, Packaging, and Handling

Atezolizumab will be supplied by the Sponsor as sterile liquid in 20-mL glass vials. The vial is designed to deliver 20 mL (1200 mg) of atezolizumab solution, but may contain more than the stated volume to enable delivery of the entire 20 mL volume.

Atezolizumab will be supplied by the Sponsor as sterile liquid in 20-mL glass vials.

For information on the formulation and handling of atezolizumab, refer to the Atezolizumab Investigator's Brochure and Pharmacy Manual.

4.3.2 Dosage, Administration, and Compliance

The dose of atezolizumab in this study will be 1200 mg (equivalent to an average body weight-based dose of 15 mg/kg) administered by intravenous infusion every 3 weeks (21 [\pm 5] days).

Administration of atezolizumab will be performed in a setting with emergency medical facilities and staff who are trained to monitor for and respond to medical emergencies. For detailed information on drug preparation, storage and administration, refer to the Atezolizumab Investigator's Brochure.

The initial dose of atezolizumab will be administered over 60 (\pm 15) minutes. If the first infusion is tolerated without infusion-associated AEs, the second infusion may be delivered over 30 (\pm 10) minutes. If the 30-minute infusion is well tolerated, all subsequent infusions may be delivered over 30 (\pm 10) minutes. For the first infusion, the patient's vital signs (heart rate, respiratory rate, blood pressures, and temperature) should be determined within 60 minutes before, during (every 15 [\pm 5] minutes if clinically indicated), and 30 (\pm 10) minutes after the infusion. For subsequent infusions, vital signs will be collected within 60 minutes before the infusion, during the infusion if clinically indicated, and 30 minutes (\pm 10 minutes) after the infusion if clinically indicated or patient experienced symptoms during previous infusions.

Patients will be informed about the possibility of delayed post-infusion symptoms and instructed to contact their study physician if they develop such symptoms.

No premedication will be allowed for the first dose of atezolizumab. Premedication may be administered for Cycles \geq 2 at the discretion of the treating physician. The management of infusion-related reactions will be according to severity as follows:

- In the event that a patient experiences a mild (Grade 1) National Cancer Institute Common Terminology Criteria for Adverse Events (NCI CTCAE) infusion-related event, the infusion rate should be reduced to half the rate being given at the time of event onset. Once the event has resolved, the investigator should wait for 30 minutes while delivering the infusion at the reduced rate. If tolerated, the infusion rate may then be increased to the original rate
- In the event that a patient experiences a moderate infusion-related event (NCI CTCAE Grade 2) or flushing, fever, or throat pain, the patient should have his or her infusion immediately interrupted and should receive aggressive symptomatic treatment. The infusion should be restarted only after the symptoms have adequately resolved to baseline grade. The infusion rate at restart should be half of the infusion rate that was in progress at the time of the onset of the infusion-related event
- For severe or life-threatening infusion-related events (NCI CTCAE Grade 3 or 4), the infusion should be stopped immediately, and aggressive resuscitation and supportive measures should be initiated. Patients experiencing severe or life-threatening infusion-related events will not receive further infusion and will be further managed as clinically indicated until the event resolves

For anaphylaxis precautions, see [Appendix 6](#).

Guidelines for dosage modification, treatment interruption or discontinuation, and the management of specific adverse events are provided in Section 5.1.2.

Each AE associated with a special situation should be recorded on the Adverse Event eCRF.

Please refer to the Pharmacy Manual for detailed instructions on drug preparation, storage and administration.

4.3.3 Investigational Medicinal Product Accountability

IMP required for completion of this study (atezolizumab) will be provided by the Sponsor. The study site is responsible for maintaining records of IMP delivery to the site, IMP inventory at the site, IMP use by each patient, and disposition or return of unused IMP, thus enabling reconciliation of all IMP received, and for ensuring that patients are provided with doses specified by the protocol.

The study site should follow all instructions included with each shipment of IMP. The study site will acknowledge receipt of IMP using the interactive response system (IxRS) to confirm the shipment condition and content. Any damaged shipments will be replaced. The investigator or designee must confirm that appropriate temperature conditions have been maintained during transit, either by time monitoring (shipment arrival date and time) or temperature monitoring, for all IMPs received and that any discrepancies have been reported and resolved before use of the IMPs. All IMPs must be stored in a secure, environmentally controlled, and monitored (manual or automated) area in accordance with the labeled storage conditions, with access limited to the investigator and authorized staff.

Only patients enrolled in the study may receive IMPs, and only authorized staff may supply or administer IMPs.

IMP will either be disposed of at the study site according to the study site's institutional standard operating procedure or returned to the Sponsor with the appropriate documentation. The site's method of IMP destruction must be agreed to by the Sponsor. The site must obtain written authorization from the Sponsor before any IMP is destroyed, and IMP destruction must be documented on the appropriate form.

Accurate records of all IMP received at, dispensed from, returned to, and disposed of by the study site should be recorded on the Drug Inventory Log.

Refer to the pharmacy manual and/or the atezolizumab Investigator's Brochure for information on IMP handling, including preparation and storage, and accountability.

4.3.4 Continued Access to Atezolizumab

The Sponsor will offer continued access to Sponsor study drug (atezolizumab) free of charge to eligible patients in accordance with the Roche Global Policy on Continued Access to Investigational Medicinal Product, as outlined below.

A patient will be eligible to receive Sponsor study drug (atezolizumab) after completing the study if all of the following conditions are met:

- The patient has a life-threatening or severe medical condition and requires continued Sponsor study drug treatment for his or her well-being
- There are no appropriate alternative treatments available to the patient
- The patient and his or her doctor comply with and satisfy any legal or regulatory requirements that apply to them

A patient will not be eligible to receive Sponsor study drug (atezolizumab) after completing the study if any of the following conditions are met:

- The Sponsor study drug is commercially marketed in the patient's country and is reasonably accessible to the patient (e.g., is covered by the patient's insurance or wouldn't otherwise create a financial hardship for the patient)
- The Sponsor has discontinued development of the drug or data suggest that the drug is not effective for non-small cell lung cancer
- The Sponsor has reasonable safety concerns regarding the drug as treatment for non-small cell lung cancer
- Provision of the drug is not permitted under the laws and regulations of the patient's country

The Roche Global Policy on Continued Access to Investigational Medicinal Product is available at the following Web site:

http://www.roche.com/policy_continued_access_to_investigational_medicines.pdf

4.4 CONCOMITANT THERAPY

Concomitant therapy consists of any prescription medications or over-the-counter preparations (e.g., prescription drugs, over-the-counter drugs, vaccines, herbal or homeopathic remedies, nutritional supplements) used by a patient in addition to protocol-mandated treatment from 7 days preceding the screening evaluation to the treatment discontinuation visit. All such medications should be reported to the investigator and recorded on the Concomitant Medications eCRF.

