- b. Response will be assessed by the investigator using RECIST v1.1 (see [Appendix 2](#)) and modified RECIST (see [Appendix 3](#)). Patients who continue atezolizumab treatment beyond radiographic disease progression assessed per RECIST v1.1 will be monitored with a follow-up scan at the next scheduled tumor assessment when the scan frequency is every 6 weeks, and will be assessed by modified RECIST criteria (see [Appendix 3](#)) until treatment discontinuation. If the scan frequency is every 9 weeks (see [Appendix 1](#)), a follow-up scan is recommended at 9 weeks or earlier if clinically indicated.
- c. In those patients for whom tumor assessments are performed as part of local clinical practice and are available for report after PD or atezolizumab treatment discontinuation, best overall response (BOR) and PFS will be assessed from the first date of the new anticancer therapy to the end of the study per RECIST v1.1 and modified RECIST.

The primary objective of the study is to evaluate the long-term safety of atezolizumab. Long-term safety will be assessed by monitoring the nature, severity, duration, frequency and timing of atezolizumab-related SAEs and atezolizumab-related irAEs. An irAE is defined as any adverse event of special interest (AESI) associated with systemic corticosteroid use within 30 days of the onset date. All-causality AEs, all-causality SAEs, AEs and SAEs leading to atezolizumab interruption or discontinuation, and AESIs will also be reported, as well as causes of death, vital signs, physical findings and clinical laboratory results.

Secondary objectives will assess the efficacy of atezolizumab. The main efficacy objective will be to evaluate the OS rate 2 years after the first dose of atezolizumab.

Other efficacy objectives will include evaluation of OS, OS rate at 3 years, PFS, ORR, and DOR (additional efficacy assessments may occur on an exploratory basis). All antitumor response assessments will be based on RECIST v1.1 and modified RECIST.

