Exploratory objectives will include evaluation of the safety and efficacy of atezolizumab in patient subgroups differentiated by: presence or absence of CNS metastases at baseline; ECOG performance status; histological subtype; history of or current autoimmune disease; and prior anticancer treatment. Other exploratory and PRO outcomes will include objective response rate and progression-free survival 2 (PFS2) following start of new anticancer therapy, HR QoL as measured on the EORTC LQ-LC13, health utility score as measured on the EQ-5D-5L instrument, and expression of PD-L1 protein and cancer-related genes in tumor samples obtained before treatment. Finally, exploratory biomarkers may be assessed in tissue to assist in the potential development of new diagnostic assays and to assess biomarkers in terms of prognosis, response/resistance and safety.

Following discontinuation of study treatment, safety assessments will be conducted for 30 days after the last study drug administration or until initiation of other anti-cancer therapy (whichever occurs first). Thereafter, follow-up information on disease progression (unless this has already occurred), anti-cancer therapy and survival will be collected via telephone contact, patient medical records, and/or clinic visits approximately every 3 months until death, loss to follow-up, end of study (30 months after last patient in), patient withdrawal or study termination by the Sponsor, whichever occurs first. In addition, irAEs, SAEs and AESIs will be collected as described in Section [5.4.2](#).

In those patients for whom tumor assessments are performed as part of local clinical practice and are available for report after PD or atezolizumab treatment discontinuation, overall response rate (ORR) and progression-free survival (PFS) will be assessed from the first date of the new anticancer therapy to the end of the study. These data will be used in an exploratory fashion to assess whether prior atezolizumab treatment positively influences response to subsequent anticancer therapies.

An Independent Data Monitoring Committee (iDMC) will be established to review all AEs, irAEs, SAEs, AESIs and other cumulative safety data.

A Schedule of Assessments for this study is provided in [Appendix 1](#).

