- Concomitant use of herbal therapies is not recommended because their pharmacokinetics, safety profiles, and potential drug-drug interactions are generally unknown. However, herbal therapies not intended for the treatment of cancer may be used during the study at the discretion of the investigator.

All concomitant medications should be reported to the investigator and recorded on the appropriate eCRF.

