5. ASSESSMENT OF SAFETY

5.1 SAFETY PLAN

The safety plan for patients in this study is derived from clinical experience with atezolizumab in completed and ongoing studies. The anticipated important safety risks are outlined below (see Section 5.1.1).

Measures will be taken to ensure the safety of patients participating in this study, including the use of carefully chosen inclusion and exclusion criteria and close monitoring of patients during the study. Administration of atezolizumab will be performed in a monitored setting in which there is immediate access to trained personnel and adequate equipment and medicine to manage potentially serious reactions.

After initiation of study treatment, all adverse events will be reported until 30 days after the last dose of study treatment or until initiation of new anti-cancer therapy, whichever occurs first. SAEs and adverse events of special interest will continue to be reported until 90 days after the last dose of study treatment or until initiation of new anti-cancer therapy, whichever occurs first.

Guidelines for managing anticipated adverse events, including criteria for dosage modification and treatment interruption or discontinuation, are provided below (Section 5.1.2), in [Appendix 9](#) and in the Atezolizumab Investigator's Brochure. Refer to Sections 5.2–5.6 for details on safety reporting during the study.

Patients with active infection are excluded from study participation. In the setting of a pandemic or epidemic, screening for active infections (including SARS-CoV-2) prior to and during study participation should be considered according to local or institutional guidelines or guidelines of applicable professional societies (e.g., American Society of Clinical Oncology or European Society for Medical Oncology).

Severe COVID-19 appears to be associated with a CRS involving the inflammatory cytokines IL-6, IL-10, IL-2, and IFN- γ (86). If a patient develops suspected CRS during the study, a differential diagnosis should include COVID-19, which should be confirmed or refuted through assessment of exposure history, appropriate laboratory testing, and clinical or radiologic evaluations per investigator judgment. If a diagnosis of COVID-19 is confirmed, the disease should be managed as per local or institutional guidelines.

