5.3.1 Adverse Event Reporting Period

Investigators will seek information on adverse events at each patient contact. All adverse events, whether reported by the patient or noted by study personnel, will be recorded in the patient's medical record and on the Adverse Event eCRF.

After informed consent has been obtained **but prior to initiation of study drug**, only serious adverse events caused by a protocol-mandated intervention (e.g., invasive procedures such as biopsies, discontinuation of medications) should be reported (see Section 5.4.2 for instructions for reporting serious adverse events).

After initiation of study drug, all adverse events will be reported until 30 days after the last dose of study drug and 90 days for serious adverse events or adverse events of special interest.

Instructions for reporting adverse events that occur after the adverse event reporting period are provided in Section 5.6.

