5.4.2.2 Events That Occur after Study Drug Initiation

After initiation of study drug, all adverse events will be reported until 30 days after the last dose of study drug and until 90 days for serious adverse events or adverse events of special interest. Investigators should record all case details that can be gathered immediately (i.e., within 24 hours after learning of the event) on the Adverse Event eCRF and submit the report via the electronic data capture (EDC) system. A report will be generated and sent to Roche Safety Risk Management by the EDC system.

In the event that the EDC system is unavailable, the paper Clinical Trial Serious Adverse Event/Adverse Event of Special Interest Reporting Form provided to investigators should be completed and submitted to the Sponsor or its designee immediately (i.e., no more than 24 hours after learning of the event), either by faxing or by scanning and emailing the form using the fax number or email address provided to investigators. Once the EDC system is available, all information will need to be entered and submitted via the EDC system.

Instructions for reporting serious adverse events that occur > 30 days after the last dose of study treatment are provided in Section [5.6](#).

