Schedule of Assessments (cont.)

	Screening Period		Treatment Period	Treatment Discontinuation	Follow-Up Period
	Day -28 to Day -1	Day -14 to -1	Day 1 (\pm 5 days) of each 3-week treatment cycle	\leq 30 days from last dose or at initiation of new anti-cancer therapy (whichever occurs first)	
Pregnancy test ^m		x	Every 3 cycles		
Tumor assessment ⁿ	x ^o		Every 6 weeks for 48 weeks, thereafter every 9 weeks until PD (regardless of atezolizumab discontinuation) or until loss of clinical benefit for patients treated beyond progression ^p		
EGFR/ALK testing ^q	x				
Submission of pre-treatment tumor tissue (biomarker) ^{r, s}		x ^u			
Plasma for RBR (optional) ^t		x ^u		PD	
EORTC QLQ-LC13 & EQ-5D-5L ^v			Day 1 of first 3 cycles, then with tumor assessments		
Concomitant medications ^w	x		x	x	
Adverse events ^x	x		x	x	x
Study drug infusion			x		
Survival and new anti-cancer therapy ^y				x	x

Abbreviations: aPTT: activated partial thromboplastin time; ECG: electrocardiogram; ECOG: Eastern Cooperative Oncology Group; EORTC: European Organisation for Research and Treatment of Cancer; INR: international normalized ratio; PD: progressive disease; PRO-CTCAE: Patient-Reported Outcomes Version of the Common Terminology Criteria for Adverse Events

Note: Unless otherwise indicated, assessments scheduled on the study treatment days should be performed prior to initiation of study treatment infusion.

a. Written informed consent is required for performing any study-specific tests or procedures. Results of standard-of-care tests or examinations performed prior to obtaining informed consent and within 28 days prior to study entry (except where otherwise specified) may be used for screening assessments rather than repeating such tests.

Appendix 1

Schedule of Assessments (cont.)

- b. Medical history includes surgical and cancer histories. Cancer history includes stage, date of diagnosis, prior anti-cancer treatment, EGFR/ALK status and, if available, PD-L1 status. Reproductive status and smoking history should also be captured. Demographic information includes age, sex, and self-reported race/ethnicity.

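### A steroid first started after the treatment discontinuation visit has no specified dated record, yet the irAE co-primary endpoint depends on steroid use near AESI onset and AESIs are reported to day 90

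*Protocol*

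**What the plan says.** - **Endpoint.** SAP 3.5.2 lists related immune-related AEs as one of two primary endpoints, reported as an incidence with an exact 95% confidence interval. Protocol Section 3.1, and the synopsis attached to the SAP, define an irAE as "any adverse event of special interest (AESI) associated with systemic corticosteroid use within 30 days of the onset date".
- **Medication recording.** Protocol Section 4.4 defines concomitant therapy as what is used "from 7 days preceding the screening evaluation to the treatment discontinuation visit" and sends those medications to the Concomitant Medications eCRF. Section 4.4.1 adds: "All concomitant medications should be reported to the investigator and recorded on the appropriate eCRF". In Appendix 1 the concomitant-medication row is marked at screening, treatment and treatment discontinuation, and is blank in follow-up. The adverse-event row is marked in follow-up.
- **Visit timing.** Section 3.1 places the treatment discontinuation visit no later than 30 days after the last dose. Appendix 1 adds that the start of new anti-cancer therapy brings it forward.
- **AESI reporting.** Section 5.1 continues it "until 90 days after the last dose of study treatment or until initiation of new anti-cancer therapy", whichever is earlier. Section 5.3.1 gives "30 days after the last dose of study drug and 90 days for serious adverse events or adverse events of special interest", with no stop at new therapy.
- **irAEs in follow-up.** Section 3.1 states: "In addition, irAEs, SAEs and AESIs will be collected as described in Section" 5.4.2. Section 5.4.2.2 says "Investigators should record all case details that can be gathered immediately", meaning within 24 hours of learning of the event. It names neither irAEs nor steroids.

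**The concern.** An AESI becomes an irAE only through a steroid, so classification needs the steroid's date as well as the event's. The plan follows the event to day 90 but specifies medication recording only to the discontinuation visit. Section 3.1 intends irAEs to be collected after treatment, but the section it refers to does not ask for the item that defines them.

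A missing record of a newly started steroid can only turn an irAE into a plain AESI, so this error runs downward. The exact confidence interval describes sampling error and would not reflect it. The study's purpose is long-term safety, and late events are the ones exposed. The same classification also feeds the irAE time-to-onset and duration summaries in SAP 3.5.4 and 3.5.6.

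**Working it through.** The plan gives no figure of its own on this point, so the check sets the collection windows side by side. Days are counted from the last dose.

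**Inputs**
- Steroid window around AESI onset: 30 days (Protocol 3.1; SAP Appendix 1).
- Latest discontinuation visit, and so the last specified medication record: day 30 (Protocol 3.1, 4.4, Appendix 1).
- End of routine AESI reporting: day 90 (Protocol 5.1, 5.3.1, 5.4.2.2, Appendix 1 note x).
- Planned patients: 600 (Protocol 6.1).

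**Which patients.** Section 5.1 and note x stop AESI reporting at new anti-cancer therapy; Sections 5.3.1 and 5.4.2.2 do not. For patients who start no new therapy, all four agree on day 90. The calculation is limited to them.

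**Onset after the visit.** Reportable onset days with no specified recording of a newly started steroid: 90 − 30 = 60, that is days 31 to 90. An earlier visit lengthens this by the same number of days.

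**Onset before the visit.** For onset on day d, with d from 1 to 30, a steroid can qualify up to day d + 30. Since d + 30 > 30 for every such d, a qualifying steroid can start after the visit. Appendix 9 shows that a delay between onset and steroid start is foreseen: for Grade 2 hepatic events and Grade 2 diarrhea or colitis, steroid treatment is tied to events lasting more than 5 days (or, for diarrhea or colitis, recurring). An AESI whose steroid starts before the visit is captured.

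**What is on record.** A steroid still in use at the visit is already on the Concomitant Medications eCRF with its start date. What is missing is new starts after the visit, and later stop dates.

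**Coverage needed.** Onset to day 90 plus a 30-day window: 90 + 30 = day 120. Specified recording ends by day 30, so 120 − 30 = 90 further days would be covered by the fix.

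**Size.** One missed patient changes the incidence by 1/600 = 0.17 percentage points. Incidence counts patients, so a patient with another captured related irAE does not change it. The number of patients missed cannot be derived. Every related irAE is a related AESI, so the related-AESI table in SAP 3.5.3 is a ceiling on the true count.

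**The case against.** **Other routes may hold the steroid.** The eCRF specifications are a separate document (Section 7.1). AESIs are reported with case details within 24 hours. Section 5.4 requires updates on the clinical course, Section 5.5.1 follows each event to resolution or stability, and Section 5.5.2 lets the sponsor query details. This stands in part: a reader might infer that late steroid data are not collected, and the documents do not show that. But none of these sections asks for dated steroid records, so the supportable statement is that such a record is not specified.

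**Days 31 to 90 are not empty.** A reader might infer that these onset days have no steroid information at all. That goes too far. Steroids ongoing at the visit are recorded, and the protocol foresees both tapers of at least a month and chronic steroid use in some patients. The gap concerns new starts.

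**Truncation is not a loss rate.** A reader might take the share of the 30-day window falling after the visit as the share of irAEs lost. The documents do not support this, because a single dated entry within the window classifies the event.

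**The consequence is limited.** The trial is descriptive. Missed events still appear among related AESIs (SAP 3.5.3), late AESIs are tabulated without a steroid condition (SAP 3.5.5), and any that are serious and related count in the other primary endpoint. This stands as a bound. It does not restore the irAE count, and SAP 3.5.5 has no late-irAE table that would reveal a loss.

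**Conclusion.** The point holds in a narrow form. Followed as written, the recording rule can leave related AESIs out of a co-primary endpoint when their systemic corticosteroid first starts after the discontinuation visit. The exposed period is 60 onset days (31 to 90) for a visit on day 30, plus onsets shortly before the visit with a later steroid start.

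This assumes that the patient starts no new anti-cancer therapy and that no form outside these documents captures the steroid. The direction is downward. The magnitude is not derivable, and any percentage loss would be an assumption.

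A reader might also infer an over-count from steroids ongoing at an unchanged baseline dose. The documents leave that rule unstated, as they do whether the 30 days run before onset, after it, or both. These are missing details, not demonstrated errors. The collection gap merits correction because the endpoint is primary and the remedy is cheap.

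**What to change.** 1. Amend Protocol Section 4.4 and Appendix 1 so that systemic corticosteroid start and stop dates and indication are recorded for every reported AESI through 30 days after its onset (to day 120 for the 90-day window). Back-fill late AESIs already reported where records allow. If an existing form holds these data, name it instead.
2. State in SAP 3.5.2 that irAEs are derived from those records.
3. As minor clarifications in the same place, give the direction of the 30-day window and say whether steroids ongoing at an unchanged baseline dose count.

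**Cost.** A small eCRF extension, a limited back-fill and a few lines in the SAP, with no new visits or patients. Back-filled dates may be incomplete, and the reported irAE incidence may shift slightly.

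**Separate item.** After the reporting period, Appendix 1 note x asks for related SAEs or AESIs, while Section 5.6 asks only for related serious events. The two should be reconciled.
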